#### 5.2.4. Preparation, Handling, and Storage

Staff at each clinical study center and the healthcare professional will be responsible for preparation of lumasiran doses, according to procedures detailed in the Pharmacy Manual. In cases where lumasiran is administered at home by a caregiver, dosing may be prepared and administered by the caregiver according to procedures detailed in the Patient/Caregiver Storage and Administration Instructions. No special procedures for the safe handling of study drug are required.

Study drug will be stored upright and refrigerated at approximately  $[5\pm 3^\circ\text{C}]$ .

A Sponsor representative or designee will be permitted, upon request, to audit the supplies, storage, dispensing procedures, and records.

Instructions specific to unused study drug and additional storage will be provided in the Pharmacy Manual and Patient/Caregiver Storage and Administration Instructions.

### **5.2.5. Packaging and Labeling**

All packaging, labeling, and production of study drug will be in compliance with current Good Manufacturing Practice specifications, as well as applicable local regulations. Study drug labels and external packaging will include all appropriate information as per local labeling requirements. Additional details will be available in the Pharmacy Manual.

### **5.2.6. Accountability**

The Investigator or designee will maintain accurate records of receipt and the condition of the study drug supplied for this study, including dates of receipt. In addition, accurate records will be kept of when and how much study drug is dispensed and administered to each patient in the study. Any reasons for departure from the protocol dispensing regimen must also be recorded.

At the completion of the study, there will be a final reconciliation of all study drugs. Used, partially used, and unused study drug will be returned to the Sponsor (or designee) or destroyed at the clinical study center according to applicable regulations.

Further instructions about drug accountability will be detailed in the Pharmacy Manual.

## **5.3. Concomitant Medications and Procedures**

Use of concomitant medications and procedures will be recorded on the patient's CRF as specified in the Schedules of Assessment (see [Table 1](#), [Table 2](#), [Table 3](#), and [Table 4](#)). This includes all prescription medications, vaccines, herbal preparations, over the counter medications, vitamins, and minerals. Any changes in medications during the study must be recorded on the CRF. Patients should not start new medication regimens during the study, including regimens of vitamins or herbal medication, without consultation with the Investigator.

If patients use nonsteroidal anti-inflammatory drugs intermittently or chronically, they must have been able to tolerate them with no previous side effects (eg, gastric distress or bleeding).

Standard vitamins and topical medications are permitted. However, topical steroids must not be applied anywhere near the injection site(s) unless medically indicated.

If taking pyridoxine (vitamin B6) for the treatment of PH1, patients must have been on a stable regimen for at least 90 days before screening and remain on this stable regimen during the screening period and through at least the Month 6 visit. Dose adjustments for interval weight gain are permitted. Patients should avoid high dose vitamin C preparations within 4 days prior to oxalate assessments.

Patients may be treated for PH1 according to local standard of care. Patients should continue their current standard of care regimen, including hyperhydration, crystallization inhibitors, and/or pyridoxine therapy at least until the Month 6 visit. Standard of care treatment may be adjusted after Month 6 in accordance with clinical judgement. If pyridoxine therapy is discontinued, pyridoxine levels should be assessed for at least the next 2 timepoints indicated in the Schedules of Assessment. Consultation with the Medical Monitor is required if treated with any new emerging products.

For other permitted concomitant medications administered subcutaneously, do not administer in same injection site area as the study drug, for at least 7 days after the last dose of study drug.

Any concomitant medication that is required for the patient's welfare may be administered by the Investigator. However, it is the responsibility of the Investigator to ensure that details regarding the medication are recorded on the CRF. Concomitant medication will be coded using an internationally recognized and accepted coding dictionary.

## 5.4. Treatment Compliance

Compliance with study drug administration will be verified by study staff.

## 5.5. Other Requirements

### 5.5.1. Contraception

Females who experience menarche during the course of the study should be asked to commit to true sexual abstinence for the remainder of their study participation and for 90 days after last dose administration. If a patient instead prefers to initiate contraception, the Investigator must approve the selected method.

Birth control methods which are considered highly effective include:

- Placement of an intrauterine device.
- Placement of an intrauterine hormone-releasing system.
- Bilateral tubal occlusion.
- Surgical sterilization of male partner (with the appropriate post-vasectomy documentation of the absence of sperm in the ejaculate; for female patients on the study, the vasectomized male partner should be the sole partner for that patient).
- Established use of oral (except low-dose gestagens), implantable, injectable, or transdermal hormonal methods of contraception.
- True sexual abstinence, when in line with the preferred and usual lifestyle of the patient. Periodic abstinence (eg, calendar, ovulation, symptothermal, post-ovulation methods) and withdrawal are not acceptable methods of contraception. Abstinent patients must agree to use one of the above-mentioned contraceptive methods, if they start heterosexual relationships during the study and for up to 90 days after the last dose of study drug.

Investigators should advise females of childbearing potential of the most appropriate birth control method available within their country taking into account local medical practice.

For male patients, no contraception is required. However, use by adolescent males of contraception (condom) may be required in some countries, eg, France, in order to comply with local requirements as described in the corresponding patient informed consent forms.

The Investigator will ensure that adolescent patients, and their legal representatives if applicable, are adequately informed about contraceptive requirements and the need for contraception once a patient initiates heterosexual intercourse. The need for contraception and compliance with

contraception requirements will be assessed at every visit for adolescent patients, and pregnancy testing will be performed before every dose for postmenarcheal females throughout the course of the study (see Section [6.5.5.2](#)).

### **5.5.2. Dietary Restrictions**

Patients should refrain from consumption of foods with high oxalate content, including, but not limited to, chocolate, rhubarb, spinach, and beet root, for 1 week prior to assessments of urinary and plasma oxalate.

## **6. STUDY ASSESSMENTS**

The schedules of study assessments are provided in [Table 1](#), [Table 2](#), [Table 3](#), and [Table 4](#). Additional information on the collection of study assessments will be detailed in the Study Manual.

Where applicable country and local regulations and infrastructure allow for home healthcare, healthcare may take place at a location other than the clinical trial site to perform study assessments, which may include collection of blood and urine samples, measurement of vital signs, length/height and weight, abbreviated physical examination/body system assessment, and preparation and administration of study drug (at the discretion of the Investigator).

### **6.1. Screening Assessments**

An informed consent form (ICF) that has been approved by the appropriate Institutional Review Board (IRB)/Independent Ethics Committee (IEC) must be signed by the legal guardian (with patient assent, as applicable) before the Screening procedures are initiated. All legal guardians will be given a copy of the signed and dated ICF and assent form, as applicable.

Patients will be screened to ensure that they meet all the inclusion criteria and none of the exclusion criteria. Rescreening of patients is permitted with consultation of the Medical Monitor (see Section [6.1.2](#)).

Patient demographic data and medical history/disease history will be obtained. Non-serious events occurring after signing of the ICF and prior to study drug administration will be captured as medical history. Any changes to medical history occurring between the screening assessment and Day 1 will be updated prior to study drug administration.

A blood sample for *AGXT* mutation analysis will be collected during screening for patients who do not have documented PH1 genetic analysis to confirm eligibility.

If serum creatinine and liver function laboratory assessments are collected greater than 30 days prior to Day 1, repeat the assessment and review results prior to initial dosing.

For all patients, single-void urine samples (in triplicate) will be collected during screening to establish baseline. In addition, for patients able to provide 24-hour urine samples, three 24-hour urine collections will be scheduled during screening to establish baseline urinary oxalate levels. 24-hour urine collections are the preferred method of evaluating urinary oxalate levels and patients are strongly encouraged to complete these collections during supervised visits unless their legal guardians are already familiar with the collection procedures. For patients unable to

provide 24-hour urine samples, a single catheterized collection will be obtained, when allowed, during screening.

#### **6.1.1. Retesting**

If in the Investigator's judgement, the screening laboratory abnormalities are likely to be transient, then laboratory tests, excluding urinary oxalate, may be repeated. The Investigator's rationale should be documented. Laboratory values can be retested once during Screening provided that the patient can be evaluated for eligibility and randomized within the allowed Screening period.

#### **6.1.2. Rescreening**

A patient who does not meet all study eligibility criteria due to a transient condition observed at Screening (eg, prohibited medications that were subsequently discontinued) may be allowed to return for rescreening after consultation with the Medical Monitor. The legal guardian will be re-consented, and assent obtained (if applicable) if rescreening occurs outside of the 60-day screening window. In this case, all screening procedures must be repeated.

### **6.2. Efficacy Assessments**

24-hour urine collections are the preferred method of evaluating urinary oxalate levels. Since not all patients will be able to provide 24-hour urine samples, single-void urine samples (in triplicate) will be collected throughout the study in all patients. [Table 9](#) shows the 24-hour urine collection procedure by study visit.

In children who are able to comply with 24-hour urine collection procedures, urinary oxalate excretion will be determined from 24-hour urine sample collections to be completed at the time points specified in the Schedules of Assessment (see [Table 1](#), [Table 2](#), [Table 3](#), and [Table 4](#)). Urinary oxalate concentrations will be analyzed centrally using a validated assay. Non-catheterized 24-hour urine collections must meet pre-specified validity criteria (see [Section 6.2.1.1](#)). The duration of collection and volume of urine in the collection will be recorded in the eCRF.

For patients who are able to comply with the 24-hour urine collection procedure, three 24-hour urine collections will be scheduled during screening to establish baseline urinary oxalate excretion. For Month 6, three 24-hour urine collections will be scheduled within 14 days prior to the Month 6 dose to evaluate changes in oxalate concentrations over the first 6-month interval. A single 24-hour collection will be scheduled at Month 12 and then every 6 months thereafter.

Patients able to comply with 24-hour urine collections will either bring a 24-hour urine collection to the clinic, courier samples to the laboratory, or have their 24-hour urine collected during an inpatient stay at the time of the study visit.

For patients who are unable to comply with 24-hour urine collections, a single catheterized 24-hour collection will be obtained, when allowed, at both baseline and Month 6. Catheterized collections may be performed at the discretion of the Investigator and with the consent of the legal guardian. Catheterized collections will be considered complete if there is no documented urine loss during the collection.

All patients will have triplicate single-void samples collected within 7 days prior to dosing, as specified in the Schedules of Assessment (see [Table 1](#), [Table 2](#), [Table 3](#), and [Table 4](#)); and either single or triplicate collections within 7 days prior to dosing as specified in the Schedules of Assessment (see [Table 3](#) or [Table 4](#)). First morning voids are the preferred sample, when feasible. Samples may be collected as an outpatient prior to the visit or collected during the study visit prior to dosing, as applicable.

**Table 9: 24-hour Urine Collection Procedure by Study Visit**

Study Visit and 24-hour Urine Collection Window	Number of 24-hour Collections	Notes
Screening (within 60-day period prior to initial dosing)	3 voided collections or 1 catheterized collection (when allowed)	Supervised 24-hour collections are encouraged unless patient/caregiver already familiar with collection procedure.
Month 6 (within 14 days prior to dosing)	3 voided collections or 1 catheterized collection (when allowed)	Supervised 24-hour collections are encouraged unless patient/caregiver already familiar with collection procedure.
Month 12 and Every 6 Months Through End of Study	1 voided collection	--

#### **6.2.1.1. Validity Criteria for Non-catheterized 24-hour Urine Collections**

A urine collection will be considered valid if each of the following criteria are met:

- The collection is between 18-26 hours in duration between the initial discarded void and the last void or attempt to void.
- No voids are missed between the start and end time of the collection.
- The 24-hour creatinine content is at least 5 mg/kg as assessed by the study central lab.

### **6.3. Pharmacodynamic and Renal Assessments**

Urine and blood samples will be collected for assessment of PD parameters (plasma and urinary oxalate and glycolate concentrations) and renal parameters at the time points specified in the Schedules of Assessment (see [Table 1](#), [Table 2](#), [Table 3](#), and [Table 4](#)). All blood and urine samples will be collected prior to dosing, if applicable. Optional collections may be performed at the discretion of the Investigator.

All PD assessments will be analyzed centrally. Pharmacodynamic assessment data will not be distributed to the sites until after the patient has completed the Month 6 visit. Site personnel should refrain from obtaining or viewing local oxalate or glycolate assessments, except as

medically indicated. Details regarding the processing and aliquoting of samples for storage and analyses will be provided in the Laboratory Manual.

Where local regulations allow, and infrastructure is in place, home nursing may be used to collect urine and blood samples.

### **6.3.1. Urinary Oxalate:Creatinine Ratio**

Urine oxalate:creatinine ratios will be calculated from the oxalate and creatinine levels measured in the 24-hour urine collections to assess the PD effect of lumasiran on urinary oxalate:creatinine ratio. Urinary oxalate:creatinine ratios from single-void urine collections will also be measured.

### **6.3.2. Estimated Glomerular Filtration Rate**

Blood samples for the assessment of eGFR will be obtained at the time points specified in the Schedules of Assessment (see [Table 1](#), [Table 2](#), [Table 3](#), and [Table 4](#)). eGFR (mL/min/1.73 m^2) will be calculated in patients  $\geq$ 12 months of age at the time of the assessment to evaluate renal function during the study. The calculation will be based on the Schwartz Bedside Formula (Appendix [10.1](#)).[Levey 2009; Schwartz 2009]

### **6.3.3. Renal Stone Events**

A renal stone event is defined as an event which includes at least one of the following:

- Visit to healthcare provider (eg, outpatient clinic, urgent care, emergency department, procedure) because of a renal stone
- Medication for renal colic
- Stone passage
- Macroscopic hematuria due to a renal stone

All relevant clinical information pertaining to the event should be obtained, including laboratory values, medical records, discharge summaries, and medical test results.

Since renal stone events are recorded as an efficacy assessment for lumasiran, these will not be treated as AEs or SAEs. However, if a patient experiences other AEs or SAEs during a renal stone event, they should be reported (see Section [6.5.6.1](#)).

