#### **4.3.4. Replacement of Study Patients**

Patients who discontinue the study drug or stop participation in the study prior to Month 6 may be replaced at the Sponsor's discretion, and the analysis of data collection prior to discontinuation is addressed in the statistical analysis plan. Patients who discontinue the study drug or stop participation in the study after Month 6 will not be replaced.

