## 6.5.6. Adverse Events

### 6.5.6.1. Definitions

#### Adverse Event

According to the ICH E2A guideline Definitions and Standards for Expedited Reporting, and 21 CFR 312.32, IND Safety Reporting, an AE is any untoward medical occurrence in a patient or clinical investigational subject administered a medicinal product and which does not necessarily have a causal relationship with this treatment.

Renal stone events (as defined in Section 6.3.3) are recorded for efficacy assessment of lumasiran. These events will not be treated as AEs or SAEs. Other AEs or SAEs occurring during a renal stone event are reported.

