#### Serious Adverse Event

An SAE is any untoward medical occurrence that at any dose:

- Results in death
- Is life-threatening (an event which places the patient at immediate risk of death from the event as it occurred. It does not include an event that had it occurred in a more severe form might have caused death)
- Requires inpatient hospitalization or prolongation of existing hospitalization
- Results in persistent or significant disability or incapacity
- Is a congenital anomaly or birth defect
- Is an important medical event that may not be immediately life-threatening or result in death or hospitalization but may jeopardize the patient and may require intervention to prevent one of the other outcomes listed in the definition above (eg, events include allergic bronchospasm requiring intensive treatment in an emergency room or at home, blood dyscrasias, convulsions, or the development of drug dependency or abuse).

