4. PATIENT POPULATION

4.1. Patient Definitions

The populations (analysis sets) are defined as follows:

- Safety Analysis Set: All patients who received any amount of lumasiran during study.
- Efficacy Analysis Set: All patients who received any amount of lumasiran and have at least one valid spot urinary UOx:Cr ratio value at baseline and at least one valid spot urinary UOx:Cr ratio value from assessment(s) at Month 3 through Month 6.
- Primary Interim Efficacy Analysis Set: Among first 16 enrolled patients, all patients who received any amount of lumasiran and have at least one valid spot urinary UOx:Cr ratio value at baseline and at least one valid spot urinary UOx:Cr ratio value from assessment(s) at Month 3 through Month 6
- PK Analysis Set: All patients who received one full dose of lumasiran and have at least one postdose blood sample for PK parameters and have evaluable PK data.

The Safety Analysis Set will be used for safety analyses and sensitivity analysis of efficacy. The Efficacy Analysis Set will be used to evaluate efficacy endpoints. The PK Analysis Sets will be used to conduct PK analyses of plasma lumasiran concentrations.

The primary analysis period is defined as the time period from the date/time of the first lumasiran dose administration until either the date/time of lumasiran dose administration at Month 6 or the date of the Month 6 visit (Day 169) for patients who discontinued treatment prematurely. Primary analysis will be conducted using all data collected in the Primary Analysis Period. All data up to the dosing at the Month 6 visit will be included in the Primary Analysis Period.

The extension period starts after the date/time of lumasiran dose administration at Month 6 until the end of the study. Analysis of Extension Phase will focus on long-term efficacy of lumasiran.

Duration of Study is defined as the time period from on or after the first date/time of lumasiran dose until the end of the study. Analyses of Duration of Study will summarize secondary endpoints using data collected during the entire study period. These analyses focus on long-term efficacy and safety effects of lumasiran during both the primary analysis period and the extension period.

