7.4. Exploratory Efficacy Analysis

Efficacy exploratory endpoints will be analyzed using the Efficacy Analysis Set generally.

To evaluate the changes in nephrocalcinosis, a renal ultrasound will be performed at baseline and 6, 12, 24, 36, 48 and 60 months. The ultrasound will measure the grade of medullary nephrocalcinosis (range: 0 to 3) where a higher grade indicates greater severity.

Changes in the grade of medullary nephrocalcinosis will be categorized in 3 groups ('no change', 'worsening' or 'improving'). Shifts in the grade of nephrocalcinosis from baseline to each post-baseline visit will be summarized. The distribution of patients by extent of change in nephrocalcinosis grade (i.e., number of grades by which nephrocalcinosis improved or worsened) from baseline to each post-baseline visit will also be summarized. At each post-baseline visit, the number and associated

percentage of patients in the following 4 categories of the overall change (i.e., accounting for both kidneys), 'no change', 'improving', 'worsening', and 'indeterminate (one kidney improving and one worsening)' will be presented. Descriptive statistics will also be generated.

To evaluate the changes in renal stone events, these events will be captured at baseline (i.e. historical information) and throughout the study. A renal stone event is defined as an event which includes at least one of the following: visit to health care provider because of a renal stone, medication for renal colic, stone passage, and macroscopic hematuria due to a renal stone.

Total number of patients with a renal stone event, total number of renal stone events and rate of renal stone events during each study period will be calculated. The rate is calculated as total

number of renal stone events divided by total number of on-study days of patients during the respective period. And 95% confidence intervals will be presented.

Changes in other PD markers (such as spot urinary and plasma glycolate) will be explored. Descriptive statistics of actual, absolute change and percent change in levels of these markers will be generated at baseline and each post-baseline visit (as applicable).

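### The SAP plans no Safety Analysis Set summary of renal stone events, so stones in a treated child without a valid Month 3–6 urine ratio would by default be shown only in listings

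*Protocol*

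**What the plan says.** **Safety reporting.** Protocol 6.3.3 counts a renal stone event when any one of four things happens: a healthcare visit because of a stone (the examples include the emergency department and procedures), medication for colic, passage of a stone, or visible blood in the urine from a stone. It then says: "Since renal stone events are recorded as an efficacy assessment for lumasiran, these will not be treated as AEs or SAEs". Protocol 6.5.6.1 repeats the exclusion and adds: "Other AEs or SAEs occurring during a renal stone event are reported". One of the seriousness criteria in the same section is "Requires inpatient hospitalization or prolongation of existing hospitalization".

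**Stone summary.** SAP 7.4 opens with "Efficacy exploratory endpoints will be analyzed using the Efficacy Analysis Set generally". Its stone paragraph plans "Total number of patients with a renal stone event, total number of renal stone events and rate of renal stone events during each study period", with 95% confidence intervals. The rate is events divided by on-study days. That paragraph names no analysis set.

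**Analysis sets.** Under SAP 4.1 the Efficacy Analysis Set needs any dose of lumasiran, a valid baseline spot ratio, and "at least one valid spot urinary UOx:Cr ratio value from assessment(s) at Month 3 through Month 6". The same section says: "The Safety Analysis Set will be used for safety analyses and sensitivity analysis of efficacy". The list of sensitivity analyses in SAP 7.1.1 applies the Safety Analysis Set only to the spot ratio. SAP 7.3 presents eGFR in both sets.

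**The concern.** Two rules that are each reasonable combine badly. Calling stones an efficacy measure removes them from the adverse event tables, which cover every treated child. Placing them under the exploratory efficacy heading then gives them a set that depends on data collected about three to six months after the first dose. A child who is treated and provides no qualifying ratio falls between the two.

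This matters because Protocol 1.1 names an obstructive stone among the events that can cause acute or chronic worsening, and because there is no control arm against which to judge the on-treatment rate.

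A second gap does not depend on early leavers. The planned stone summary counts a stone passed at home and a stone needing a procedure or admission as one event each. The serious adverse event tables cannot make the distinction, because the stone itself never enters them. The same holds for the table of adverse events leading to treatment discontinuation in SAP 7.7.1.

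**Working it through.** The plan states no figure to reproduce. The check is mainly one of set logic, followed by an illustration of scale.

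**Step 1: where a stone event is tabulated.**

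| Child | Adverse event tables (Safety Analysis Set) | Stone table (SAP 7.4 default) | Listings |
|---|---|---|---|
| Treated, with a valid baseline ratio and a valid Month 3–6 ratio | Stone excluded; other events during it included | Included | Included |
| Treated, without a qualifying ratio | Stone excluded; other events during it included | Not included | Included |

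The baseline requirement should rarely bite, because inclusion criterion 3 (Protocol 4.1) already needs screening spot ratios. The Month 3–6 requirement is the one that selects.

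**Step 2: who is in the second row.** The condition is having no qualifying ratio, not stopping drug early.
- A child who stops drug is encouraged to complete assessments through Month 6 (Protocol 4.3.1), and SAP 5.5 uses data from after discontinuation.
- A child leaving all follow-up should have the Month 6 assessments brought forward (Protocol 4.3.2.1). SAP 5.6 analyses by the visit label on the eCRF, so a sample labelled Month 6 could qualify that child.
- The affected child is the one for whom no such sample is obtained, or whose sample is invalid or labelled otherwise.

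**Step 3: how likely it is that such a child exists.** With 20 treated patients and an assumed probability p that a child has no qualifying ratio, the chance of at least one is 1 − (1 − p)^20:
- p = 1%: 18%
- p = 2.5%: 40%
- p = 5%: 64%
- p = 10%: 88%

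The documents give no value for p.

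**Step 4: effect on the rate if that child had one stone event.** Assume 19 children in the Efficacy Analysis Set for 168 days each (Month 6 is Day 169). That is 19 × 168 = 3,192 days, or 3,192 / 365.25 = 8.74 patient-years. Add one treated child who leaves between Day 28 and Day 84 after one event, giving 3,220 to 3,276 days. The rate is events / days × 365.25.

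| Events in the other 19 (assumed) | Efficacy Analysis Set | Safety Analysis Set |
|---|---|---|
| 0 | 0.00 | 1/3,276 to 1/3,220 days: 0.11 |
| 1 | 1/3,192 days: 0.11 | 2/3,276 to 2/3,220 days: 0.22 to 0.23 |
| 3 | 3/3,192 days: 0.34 | 4/3,276 to 4/3,220 days: 0.45 |

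The shift is 0.10 to 0.11 per patient-year in each row.

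**Step 5: effect if that child had no stone event.** Exclusion then removes only person-time. With 3 events in the others and an exit at Day 84, the Safety Analysis Set rate is 3 / 3,276 × 365.25 = 0.334, against 0.343 in the Efficacy Analysis Set. Exclusion now raises the rate, by about 0.01. The sign depends on what happened to the missing child.

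**The case against.** A reader might infer that stones are confined to the Efficacy Analysis Set, that any child leaving before Month 3 is lost, and that such a case disappears from every output. The documents do not go that far:
- SAP 7.4 uses the word *generally*, and the stone paragraph names no set. A Safety Analysis Set table is not ruled out; it is simply not planned.
- Leaving before Month 3 is not the test, as Step 2 shows.
- Other adverse events during a stone event reach the safety tables. Concomitant medications are summarised in the Safety Analysis Set (SAP 6.4), discontinuations are tabulated with reasons (SAP 6.1), and all CRF data are listed (SAP 5.2). With 20 patients a single case can be read individually. A replaced child remains in the Safety Analysis Set.
- Renal worsening is also followed through eGFR, summarised in both sets, and through nephrocalcinosis shifts.

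A reader might also infer a sizeable downward bias. At assumed rates of 0.25 to 1.0 per patient-year, 8.74 patient-years give 2.2 to 8.7 counted events, and one missed event is 1/(2.2 + 1) = 31% down to 1/(8.7 + 1) = 10% of the total. That calculation stipulates the event it then counts. Under the same constant-rate assumption, a child leaving at Day 84 contributes only 84/3,276 = 2.6% of expected events.

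Finally, the endpoint is exploratory and the analysis descriptive, and the content of the DMC reports lies in a charter outside these documents, so no gap there can be shown.

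All of this narrows the point. What stands is that a listing is not a summary, a medication table does not identify a stone event, and SAP 4.1 assigns efficacy endpoints to the Efficacy Analysis Set without qualification. Since the SAP gives eGFR both sets, doing the same for stones would be no departure from its own practice.

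**Conclusion.** The point holds in a limited form. By default, the stone count and rate are conditioned on a post-baseline requirement, and a stone event in a treated child without a qualifying ratio is seen only in listings, apart from accompanying adverse events and medications. Separately, no planned table distinguishes stone events that meet a seriousness criterion from minor ones, even among children who stay.

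The direction and size of any bias cannot be derived from the documents. The figure of about 0.1 per patient-year for the 6-month rate assumes one affected child, one stone event in that child, and full 168-day follow-up in the other 19. Over the longer extension the same single event would weigh less. The case for acting rests on the selection rule and the low cost of removing it, not on a demonstrated distortion.

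**What to change.** - **SAP 7.4:** state that renal stone events (patients, events, and rate with confidence interval) are analysed in the Safety Analysis Set, with all treated patients' on-study days from first dose as the denominator. Membership then no longer depends on whether an exit sample was obtained or how it was labelled.
- **SAP 7.7.1:** add one Safety Analysis Set table or listing of stone events that met a protocol seriousness criterion, required a procedure, or led to discontinuation.

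The convention that stone events are not adverse events can stay. No new data collection should be needed, since Protocol 6.3.3 already asks for medical records and discharge summaries for each event. The cost is a sentence of SAP text, one extra output, and possibly a slightly less favourable stone rate if children without a qualifying ratio had events.
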